## 2. Injection Site Reactions

VIVITROL must be prepared and administered by a healthcare provider. VIVITROL injections may be followed by pain, tenderness, induration, swelling, erythema, bruising, or pruritus; however, in some cases injection site reactions may be very severe. In the clinical trials, one patient developed an area of induration that continued to enlarge after 4 weeks, with subsequent development of necrotic tissue that required surgical excision. In the postmarketing period, additional cases of injection site reaction with features including induration, cellulitis, hematoma, abscess, sterile abscess, and necrosis, have been reported. Some cases required surgical intervention, including debridement of necrotic tissue. Some cases resulted in significant scarring. The reported cases occurred primarily in female patients.

VIVITROL is administered as an intramuscular gluteal injection, and inadvertent subcutaneous injection of VIVITROL may increase the likelihood of severe injection site reactions. The needles provided in the carton are customized needles. VIVITROL must not be injected using any other needle. The needle lengths (either 1 1/2 or 2 inches) may not be adequate in every patient because of body habitus. Body habitus should be assessed prior to each injection for each patient to assure that the proper needle is selected and that the needle length is adequate for intramuscular administration. For patients with a larger amount of subcutaneous tissue overlying the gluteal muscle, the administering healthcare provider may utilize the supplied 2-inch needle with needle protection device to help ensure that the injectate reaches the intramuscular mass. For very lean patients, the 1 1/2-inch needle may be appropriate to prevent the needle contacting the periosteum. Either needle may be used for patients with average body habitus. Healthcare providers should ensure that the VIVITROL injection is given correctly, and should consider alternate treatment for those patients whose body habitus precludes an intramuscular gluteal injection with one of the provided needles.

Patients should be informed that any concerning injection site reactions should be brought to the attention of the healthcare provider. Patients exhibiting signs of abscess, cellulitis, necrosis, or extensive swelling should be evaluated by a physician to determine if referral to a surgeon is warranted.

### 3. Precipitation of Opioid Withdrawal

The symptoms of spontaneous opioid withdrawal (which are associated with the discontinuation of opioid in a dependent individual) are uncomfortable, but they are not generally believed to be severe or necessitate hospitalization. However, when withdrawal is precipitated abruptly by the administration of an opioid antagonist to an opioid-dependent patient, the resulting withdrawal syndrome can be severe enough to require hospitalization. Review of postmarketing cases of precipitated opioid withdrawal in association with naltrexone treatment has identified cases with symptoms of withdrawal severe enough to require hospital admission, and in some cases, management in the intensive care unit.

To prevent occurrence of precipitated withdrawal in patients dependent on opioids, or exacerbation of a pre-existing subclinical withdrawal syndrome, opioid-dependent patients, including those being treated for alcohol dependence, should be opioid-free (including tramadol) before starting VIVITROL treatment. An opioid-free interval of a minimum of 7–10 days is recommended for patients previously dependent on short-acting opioids. Patients transitioning from buprenorphine or methadone may be vulnerable to precipitation of withdrawal symptoms for as long as two weeks.

If a more rapid transition from agonist to antagonist therapy is deemed necessary and appropriate by the healthcare provider, monitor the patient closely in an appropriate medical setting where precipitated withdrawal can be managed.

In every case, healthcare providers should always be prepared to manage withdrawal symptomatically with non-opioid medications because there is no completely reliable method for determining whether a patient has had an adequate opioid-free period. A naloxone challenge test may be helpful; however, a few case reports have indicated that patients may experience precipitated withdrawal despite having a negative urine toxicology screen or tolerating a naloxone challenge test (usually in the setting of transitioning from buprenorphine treatment). Patients should be made aware of the risks associated with precipitated withdrawal and encouraged to give an accurate account of last opioid use. Patients treated for alcohol dependence with VIVITROL should also be assessed for underlying opioid dependence and for any recent use of opioids prior to initiation of treatment with VIVITROL. Precipitated opioid withdrawal has been observed in alcohol-dependent patients in circumstances where the prescriber had been unaware of the additional use of opioids or co-dependence on opioids.

### 4. Hepatotoxicity

Cases of hepatitis and clinically significant liver dysfunction were observed in association with VIVITROL exposure during the clinical development program and in the postmarketing period. Transient, asymptomatic hepatic transaminase elevations were also observed in the clinical trials and postmarketing period. Although patients with clinically significant liver disease were not systematically studied, clinical trials did include patients with asymptomatic viral hepatitis infections. When patients presented with elevated transaminases, there were often other potential causative or contributory etiologies identified, including pre-existing alcoholic liver disease, hepatitis B and/or C infection, and concomitant usage of other potentially hepatotoxic drugs. Although clinically significant liver dysfunction is not

typically recognized as a manifestation of opioid withdrawal, opioid withdrawal that is precipitated abruptly may lead to systemic sequelae including acute liver injury.

Patients should be warned of the risk of hepatic injury and advised to seek medical attention if they experience symptoms of acute hepatitis. Use of VIVITROL should be discontinued in the event of symptoms and/or signs of acute hepatitis.

#### 5. Depression and Suicidality

Alcohol- and opioid-dependent patients, including those taking VIVITROL, should be monitored for the development of depression or suicidal thinking. Families and caregivers of patients being treated with VIVITROL should be alerted to the need to monitor patients for the emergence of symptoms of depression or suicidality, and to report such symptoms to the patient's healthcare provider.

##### Alcohol Dependence

In controlled clinical trials of VIVITROL administered to adults with alcohol dependence, adverse events of a suicidal nature (suicidal ideation, suicide attempts, completed suicides) were infrequent overall, but were more common in patients treated with VIVITROL than in patients treated with placebo (1% vs 0%). In some cases, the suicidal thoughts or behavior occurred after study discontinuation, but were in the context of an episode of depression that began while the patient was on study drug. Two completed suicides occurred, both involving patients treated with VIVITROL.

Depression-related events associated with premature discontinuation of study drug were also more common in patients treated with VIVITROL (~1%) than in placebo-treated patients (0%).

In the 24-week, placebo-controlled pivotal trial in 624 alcohol-dependent patients, adverse events involving depressed mood were reported by 10% of patients treated with VIVITROL 380 mg, as compared to 5% of patients treated with placebo injections.

##### Opioid Dependence

In an open-label, long-term safety study conducted in the US, adverse events of a suicidal nature (depressed mood, suicidal ideation, suicide attempt) were reported by 5% of opioid-dependent patients treated with VIVITROL 380 mg (n=101) and 10% of opioid-dependent patients treated with oral naltrexone (n=20). In the 24-week, placebo-controlled pivotal trial that was conducted in Russia in 250 opioid-dependent patients, adverse events involving depressed mood or suicidal thinking were not reported by any patient in either treatment group (VIVITROL 380 mg or placebo).

#### 6. When Reversal of VIVITROL Blockade Is Required for Pain Management

In an emergency situation in patients receiving VIVITROL, suggestions for pain management include regional analgesia or use of non-opioid analgesics. If opioid therapy is required as part of anesthesia or analgesia, patients should be continuously monitored in an anesthesia care setting by persons not involved in the conduct of the surgical or diagnostic procedure. The opioid therapy must be provided by individuals specifically trained in the use of anesthetic drugs and the management of the respiratory effects of potent opioids, specifically the establishment and maintenance of a patent airway and assisted ventilation.

Irrespective of the drug chosen to reverse VIVITROL blockade, the patient should be monitored closely by appropriately trained personnel in a setting equipped and staffed for cardiopulmonary resuscitation.

## 7. Eosinophilic Pneumonia

In clinical trials with VIVITROL, there was one diagnosed case and one suspected case of eosinophilic pneumonia. Both cases required hospitalization, and resolved after treatment with antibiotics and corticosteroids. Similar cases have been reported in postmarketing use. Should a person receiving VIVITROL develop progressive dyspnea and hypoxemia, the diagnosis of eosinophilic pneumonia should be considered. Patients should be warned of the risk of eosinophilic pneumonia, and advised to seek medical attention should they develop symptoms of pneumonia. Clinicians should consider the possibility of eosinophilic pneumonia in patients who do not respond to antibiotics.

## 8. Hypersensitivity Reactions Including Anaphylaxis

Cases of urticaria, angioedema, and anaphylaxis have been observed with use of VIVITROL in the clinical trial setting and in postmarketing use. Patients should be warned of the risk of hypersensitivity reactions, including anaphylaxis. In the event of a hypersensitivity reaction, patients should be advised to seek immediate medical attention in a healthcare setting prepared to treat anaphylaxis. The patient should not receive any further treatment with VIVITROL.

## 9. Intramuscular Injections

As with any intramuscular injection, VIVITROL should be administered with caution to patients with thrombocytopenia or any coagulation disorder (e.g., hemophilia and severe hepatic failure).

## 10. Alcohol Withdrawal

Use of VIVITROL does not eliminate nor diminish alcohol withdrawal symptoms.

## 11. Interference with Laboratory Tests

VIVITROL may be cross-reactive with certain immunoassay methods for the detection of drugs of abuse (specifically opioids) in urine. For further information, reference to the specific immunoassay instructions is recommended.

12. Known side-effects from NTX include difficulty sleeping, anxiety, nervousness, abdominal pain/cramps, nausea and/or vomiting, low energy, joint and muscle pain, headache, loss of appetite, diarrhea, constipation, increased thirst, increased energy, depressive mood, irritability, dizziness, skin rash, delayed ejaculation, erection dysfunction, reduced sexual desire, and chills.
13. Naloxone injection may cause withdrawal symptoms in individuals who are opioid dependent including nausea, vomiting, diarrhea, stomach pain, fever, sweating, body aches, weakness, running nose, goosebumps, shivering, increased heart rate, and anxiety.

### **2.3.2 Known Potential Benefits**

1. There are no known potential benefits of this treatment in the study cohort.
2. There is a large potential benefit to the opiate addicted community as robust PK data will allow for the ongoing development of the OLANI product.

### 3 OBJECTIVES AND PURPOSE

#### 3.1 PRIMARY OBJECTIVES

To determine the PK parameters of  $C_{max}$ ,  $T_{max}$  and AUC for the 1st and 6th dose of Vivitrol IM 380 mg, and  $C_{trough}$  for the 1st through 6th dose.  $C_{trough}$  is defined as the naltrexone level obtained 28 days after each dose. PK parameters will be collected over a treatment period of 196 days.

Primary outcomes used to determine these properties will be based on results from plasma concentration of NTX and 6 $\beta$ N as ascertained from blood samples taken at the following time points:

- Day 0 (predose, +1, 2, 4, 8, 12 & 24 hours), 1.5, 1.75, 2, 3, 5, 7, 10, 14, 17, 21, 24, 28,
- Day 56, 84, 112 days,
- Day 140 (predose +1, 2, 4, 8 & 12 hours), 141, 141.5, 141.75, 142, 143, 145, 147, 150, 154, 157, 161, 164, 168, 182, and 196 days

#### 3.2 SECONDARY OBJECTIVES

- To confirm no accumulation between repeat doses
- To determine the safety and tolerability of Vivitrol over 196 days.

Safety endpoints will be captured throughout and will include the incidence of AEs including:

- deaths
- SAEs
- AEs leading to discontinuation
- common AEs
- AEs of special interest (injection site reactions and hepatic effects)
- laboratory abnormalities (absolute values and changes over time in laboratory parameters)
- the proportion of participants who discontinue treatment due to AEs)

## 4 STUDY DESIGN AND ENDPOINTS

### 4.1 DESCRIPTION OF THE STUDY DESIGN

Participants who have completed the study end points of GM 0017 (i.e. two consecutive monthly plasma results <0.1 ng/mL for NTX) will be offered enrolment into the study.

Up to 15 participants will be recruited onto this arm with 12 expected to complete to full dosing and sampling schedule.

Participants will receive a 380 mg Vivitrol IM injection and blood samples will be taken according to the sampling schedule of Table 7-1. Subsequently, participants will be re-administered Vivitrol injections every 28 days for a total of 6 Vivitrol injections. Blood sampling will be performed as per Table 7-1. The administration of 6 repeated Vivitrol injections is to confirm the published findings that no accumulation of Vivitrol is evident after repeated injections and to allow a direct time frame comparison to future bioequivalence study with OLANI.

This PK information, including day 28 naltrexone trough level, is needed so that Vivitrol can be used as the reference product for previous and future studies of OLANI.

### 4.2 STUDY ENDPOINTS

#### 4.2.1 *Primary Endpoint*

- The collection of at least 75% of the PK blood samples including respective day 28 blood collections for 1st and 6th injection phase.

#### 4.2.2 *Secondary Endpoints*

Safety endpoints will be captured through 6 months and will include the incidence of AEs including:

- deaths
- SAEs
- AEs leading to discontinuation
- common AEs
- AEs of special interest (injection site reactions and hepatic effects)
- laboratory abnormalities (absolute values and changes over time in laboratory parameters)
- the proportion of participants who discontinue treatment due to AEs

#### 4.2.3 *Primary Efficacy Endpoint:*

- Establishment of reference product Vivitrol 28-day naltrexone trough blood level.
- Mean Cmax, Tmax, AUC, Ctrough for NTX blood level
- Mean Cmax, Tmax, AUC, Ctrough for 6 $\beta$ N blood level

#### 4.2.4 *Secondary Efficacy Endpoints:*

- Frequency of AEs and SAEs

## 5 STUDY ENROLLMENT AND WITHDRAWAL

### 5.1 PARTICIPANT INCLUSION CRITERIA

Healthy participants without a DSM 5 - Substance Related Disorders classification will be recruited for this study. Participants will be assessed for their general health and mental health status.

Participants will be required to undergo a NCT to confirm opiate naivety before administration of the IP.

To qualify for the study participation, participants have to:

- Have completed GM 0017 (i.e. been administered OLANI (3.6 gram) and provided two consecutive monthly blood samples of NTX below 0.1 ng/mL)
- Men or women aged at least 18 ( $\geq 18$ ) and no older than 57 ( $< 58$ ), without DSM 5 - Substance Related Disorders classification; in sustained remission is not exclusionary
- Able and willing to comply with the requirements of the protocol
- Able and willing to provide written informed consent
- Willing to undergo an injection of NTX to allow for investigational drug administration in the intramuscular tissue
- Have an initial weight between 45.3 and 81.6 kilograms (inclusive) or have a BMI inclusive of 18.5 to 30.0.

### 5.2 PARTICIPANT EXCLUSION CRITERIA

Participants will not be eligible for the study if they meet any of the following criteria:

- Is currently on active NTX medication.
- Positive UDS at screening for illicit substances.
- Has a condition which requires treatment with opioid based medication.
- Has a known hypersensitivity to NTX.
- Is prone to skin rashes, irritation or has a skin condition such as recurrent eczema that is likely to impact the injection site area, or as determined by the evaluating physician.
- Demonstrates any abnormal skin tissue in the proposed injection area.
- Is pregnant or planning to be. Women need to have negative pregnancy test at screening. Women need to agree to practice an effective method of contraception throughout participation.
- Participant is breastfeeding or planning to be.
- Has a current significant neurological (including cognitive and psychiatric disorders),
- Any clinically important abnormal finding as determined by medical history, physical examination, ECG or clinical laboratory tests.
- Any additional condition(s) that in the investigator's opinion would prohibit the participant from completing the study or would not be in the best interest

of the participant.

- ALT or AST >3 times the upper end of the laboratory normal range.
- Any methadone use 14 days prior to screening, and up to Study Day 0.
- Current DSM 5 diagnosis of schizophrenia, bipolar, anxiety, or depressive disorder, confirmed by MINI assessment, or currently treated with medications for anxiety or depression. Past history (in remission DSM 5 classification) of anxiety or depression is not exclusionary.
- Any elevated risk for suicide measured using the Columbia Suicide Severity Rating Scale, endorsing any of the items in the past month (C-SSRS, Lifetime)
- Is participating or intending to participate in any other clinical trial during the duration of this study.
- Is allergic to any of the ingredients in Vivitrol or the diluent used to mix Vivitrol (i.e. carboxymethylcellulose sodium, polysorbate 20, sodium chloride, sodium hydroxide and hydrochloric acid as pH adjusters, in water for injection).

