##### 7.1.1.3 Naloxone challenge test (NCT)

All participants will undergo an NCT at Clinilabs prior to IP administration. Participants will receive 0.8 mg naloxone, IM, followed by q10 minutes observation by study clinician or nurse over 30 minutes for signs and symptoms of opiate withdrawal.

Naloxone injection may cause withdrawal symptoms such as nausea, vomiting, diarrhea, stomach pain, fever, sweating, body aches, weakness, running nose, goosebumps, shivering, increased heart rate, and anxiety. Most of these effects will wear off after 20-30 minutes and treatment is usually not needed but in case of severe symptoms, participants will be offered a dose of clonidine 0.1 mg and/or clonazepam 0.5 mg. In that case, participants will be monitored for up to 6 hours until all symptoms resolve, and they can be released.

If a participant passes the NCT then they will progress to IP administration with the injection procedure (see Section 7.1.1.4).

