## 7.5 PROHIBITED MEDICATIONS, TREATMENTS AND PROCEDURES

The medications and substances listed below are prohibited for the specified time periods:

- **Buprenorphine**, either as part of a maintenance program or any illicit/non prescribed is prohibited for the duration of the study.
- **Methadone** is prohibited at least 14 days prior to Day 0 and for the duration of the Study.
- All other **opioids** are prohibited for the duration of the study unless approved by the PI or study clinician (see section 7.7)
- **Oral naltrexone** is prohibited for at least 30 days prior to Day 0 and for the duration of the study
- **Extended release naltrexone (e.g., Vivitrol)** is prohibited for at least 60 days prior to Day 0 and for the duration of the study unless administered under this trial protocol.

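### A 14-day pre-dose interval is set for methadone but not for buprenorphine, although Section 2.3.1 gives both drugs the same two-week withdrawal warning (minor safety alignment)

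*Combined protocol and SAP*

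**What the plan says.** **Eligibility.** Section 5.2 excludes "Any methadone use 14 days prior to screening, and up to Study Day 0". It does not name buprenorphine.

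**Prohibited medications.** Section 7.5 says that methadone "is prohibited at least 14 days prior to Day 0 and for the duration of the Study". For buprenorphine it says only that use "either as part of a maintenance program or any illicit/non prescribed is prohibited for the duration of the study". The same list gives lead-in periods for oral naltrexone (30 days) and extended-release naltrexone (60 days).

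**Warning.** Section 2.3.1, item 3, taken from the product label, states: "Patients transitioning from buprenorphine or methadone may be vulnerable to precipitation of withdrawal symptoms for as long as two weeks". On the limits of testing it says that "a few case reports have indicated that patients may experience precipitated withdrawal despite having a negative urine toxicology screen or tolerating a naloxone challenge test", and qualifies this as "usually in the setting of transitioning from buprenorphine treatment".

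**Gate to dosing.** Section 7.1.1.3 requires a naloxone challenge and then states: "If a participant passes the NCT then they will progress to IP administration with the injection procedure". Section 5.4.2.1 notes that the injection cannot be removed once given.

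**The concern.** The protocol reproduces a warning about two drugs and writes an interval for only one of them. The omitted drug is the one for which the same warning says that a urine screen and a naloxone challenge are most likely to give false reassurance. A drug-free interval taken from the history depends on neither test, and only methadone has one.

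What is at stake is a precipitated withdrawal after a depot that cannot be withdrawn, in a volunteer for whom Section 2.3.2 identifies no benefit. This is a matter of eligibility wording and participant safety. It does not touch the PK parameters or their analysis.

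**Working it through.** The plan gives no figure to reproduce. The check sets the sections side by side, with one small piece of arithmetic on days.

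**Step 1. Compare the two drugs.**

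| Item | Methadone | Buprenorphine |
|---|---|---|
| Vulnerability window, Section 2.3.1 item 3 | up to two weeks | up to two weeks |
| Named in Section 5.2 | yes | no |
| Interval before Day 0, Section 5.2 | from 14 days before screening to Day 0 | none |
| Interval before Day 0, Section 7.5 | at least 14 days | none |
| Named as the usual setting for missed cases, Section 2.3.1 item 3 | no | yes |

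**Step 2. Days guaranteed drug-free at Day 0.** Let *s* be the number of days from screening to Day 0. The protocol states no minimum, so I assume a range of 0 to 28.

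- Methadone under Section 5.2: 14 + *s*. Under Section 7.5: 14.
- Buprenorphine, if the Section 7.5 ban starts at Day 0: 0.
- Buprenorphine, if the ban starts at screening: *s*.
- Shortfall against two weeks: 14 − 0 = 14 on the Day 0 reading, or max(0, 14 − *s*) on the screening reading.

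| *s* (assumed) | Methadone, Section 5.2 | Buprenorphine shortfall, Day 0 reading | Buprenorphine shortfall, screening reading |
|---|---|---|---|
| 0 | 14 | 14 | 14 |
| 7 | 21 | 14 | 7 |
| 14 | 28 | 14 | 0 |
| 28 | 42 | 14 | 0 |

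On the screening reading the gap closes once screening falls at least 14 days before dosing, but nothing in the protocol requires that spacing.

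**Step 3. Do the other criteria supply the interval?**

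- The urine exclusion in Section 5.2 concerns illicit substances at screening. Section 7.2.1 includes a buprenorphine assay, but prescribed buprenorphine is not plainly illicit. Table 7-1 repeats the urine screen at the Day 0 admission without stating what a positive result means for eligibility.
- The exclusion for conditions needing opioid treatment is in the present tense. It does not reach someone who has recently stopped.
- Section 7.3.1 judges medication history against the inclusion and exclusion criteria, which have no buprenorphine line. Section 7.4 records prescription medication back at least 90 days, so recent prescribed use should be visible.
- Section 5.2 also has two general exclusions: clinically important abnormal findings, including from the medical history, and the investigator's opinion. Either could be used to exclude such a person. Both are discretionary and neither sets a number of days.

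**Step 4. Rescue use.** Section 7.7 offers buprenorphine as a possible analgesic during the study, while its entry in Section 7.5 has no exception. The approval route to Section 7.7 is attached only to the entry for other opioids. Any rewrite of the buprenorphine entry should settle this too.

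**The case against.** The strongest reply is that the warning concerns opioid-dependent patients in transition, whereas this trial enrols healthy volunteers. To be at risk, a person would have to be one of the 19 GM 0017 completers, with two consecutive monthly naltrexone levels below 0.1 ng/mL. That person would then have to become physically dependent on buprenorphine and stop it recently, yet have no current substance-related disorder and no condition needing opioids. The person would also have to get past clinicians who review the medication history and sign the eligibility checklist, and then pass a 0.8 mg naloxone challenge. The documents give no sign that such a person exists, and the reports of missed cases are few. Study duration may also be read as beginning at screening, since Section 6.1.8 counts recruitment in the study length.

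Most of this stands, and it is why the point is minor. It does not justify treating the two drugs differently. The sponsor already applies a methadone interval to this same healthy cohort, and the discretionary criteria would cover methadone equally well. Section 5.1 allows disorders in sustained remission, and Section 7.5 itself contemplates buprenorphine maintenance.

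A reader might infer that every opioid needs a lead-in, because Section 2.3.1 also says "An opioid-free interval of a minimum of 7–10 days is recommended for patients previously dependent on short-acting opioids". The documents do not support that step. The sentence is limited to previously dependent patients, the naloxone challenge already tests for dependence, and the warning about missed cases points mainly to buprenorphine.

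**Conclusion.** The asymmetry is real and worth correcting as a cheap safety alignment, at the level of something to consider. Methadone has at least 14 guaranteed drug-free days before dosing. Buprenorphine has 0 on one reading of Section 7.5 and an unspecified number on the other. The text comparison is firm; the day counts for the screening reading rest on the assumed range of *s*.

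A reader might infer that all of the up to 15 participants are exposed to precipitated withdrawal. The documents do not support that. Only a recent buprenorphine user could be affected, no rate of such use is given, and the number may be zero. Nor is it shown that a recent user would pass every criterion: the general exclusions, the medication history and the naloxone challenge could each stop that person. The practical risk is very low, and no PK result changes.

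**What to change.** 1. In Section 5.2, add: *Any buprenorphine use (prescribed or not) within 14 days prior to Study Day 0.* Anchor it to Day 0. Anchoring it to screening, as the methadone criterion does, would demand 14 + *s* days, up to 42 at *s* = 28, which is more than the two weeks in the warning.
2. In Section 7.5, state that buprenorphine is prohibited for at least 14 days before Day 0 and throughout the study, except as rescue analgesia approved under Section 7.7.
3. Confirm compliance before the injection from the medication history, self-report and urine screen already scheduled at screening and Day 0.
4. Leave the entry for other opioids as it is.

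The cost is a few words in two sections and one line on the Day 0 checklist, with no new visit or test. The downside is that a rare participant is delayed or excluded.
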